## 11.0 APPENDIX

### Appendix 1: Schedule of assessment and procedures

[figure not shown]
Study Procedures	Screening	Pre-dose		Post-dose											
		Confinement a					Clinic Visits								
	Day -21 to Day 1	Day 1				1 wk	2 wk	4 wk	6 wk	13 wk (EOS) b	6 mth	9 mth	12 mth	18 mth	24 mth (EOS) c
		0 hr	2 hr	4 hr	6 hr	24 hr	±15 min	±1 hr	±2 days	±5 days	±1 wk	±2 wk	±4 wk		
Screening															
Informed Consent	X														
Inclusion/Exclusion	X	X													
Demographics	X														
Medical History	X														
Height (cm)	X														
Safety Assessments															
Concomitant Prior Medications	X	X					X	X	X	X	X	X	X	X	X
MRI	X									X	X	X	X	X	X
X-ray	X									X	X	X	X	X	X
Weight (kg)	X	X					X	X	X	X	X	X	X	X	X
Physical Examination	X	X	X				X	X	X	X	X	X	X	X	X
Neurologic Examination	X	X	X				X	X	X	X	X	X	X	X	X
Vital Signs	X	X	X	X	X	X	X	X	X	X	X	X	X	X	X
12-lead ECG d	X						X				X				
Clinical Laboratory Tests e	X						X	X	X		X				
Serum Pregnancy Test	X										X				
Urine Pregnancy Test f		X													
Urine Drug Screen	X														
HBsAg, anti-HCV, anti-HIV	X														
Adverse Events							◀	▶							
Investigational Product Administration															
Investigational Product Administration g		X													

Study Procedures	Screening	Pre-dose		Post-dose											
		Confinement a					Clinic Visits								
	Day -21 to Day 1	Day 1				1 wk	2 wk	4 wk	6 wk	13 wk (EOS) b	6 mth	9 mth	12 mth	18 mth	24 mth (EOS) c
		0 hr	2 hr	4 hr	6 hr	24 hr	±15 min	±1 hr	±2 days	±5 days	±1 wk	±2 wk	±4 wk		
PK and PD Sampling							X	X	X	X					
Blood Sampling for anti-KTP-001 Antibody		X													
Blood Sampling for KTP-001		X	X	X	X	X	X	X	X	X					
Blood Sampling for keratan sulfate		X			X	X	X	X	X	X					
Efficacy Assessments (exploratory)							X	X	X	X					
Dispense Study Diary	X	X					X	X	X	X					
Collect and Review Study Diary		X					X	X	X	X	X				
Lower Back Pain or Leg Pain	X	X	X	X	X	X	X	X	X	X	X h	X h	X h		
Spinal Flexion/Tension	X	X				X	X	X	X	X	X	X	X	X	
ODI	X	X				X	X	X	X	X	X	X	X	X	
SF-12	X	X				X	X	X	X	X	X	X	X	X	
PGI-C	X	X				X	X	X	X	X	X	X	X	X	

Abbreviations: PGI-C=Patient Global Impression of Improvement; ODI=Oswestry Disability Index; SF-12=Short Form 12 (QOL assessment); PK=pharmacokinetics; PD=pharmacodynamics; MRI=magnetic resonance imaging; ECG=electrocardiogram; HBsAg=hepatitis B surface antigen, HCV=hepatitis C, HIV=human immunodeficiency virus; hr = hour(s); mth = month(s); wk = week(s)

- a. 24 hours hospitalization after the intradiscal injection is performed. Discharge is based on data up to 24 hours.
- b. The same procedures as described in [Section 11.13](#) will be used for early termination prior to Week 24.
- c. The same procedures as described in [Section 11.12](#) will be used for early termination between Week 13 and Month 24.
- d. Follow-up ECG(s) will be obtained if any significant abnormalities are detected after dose administration to document resolution and as clinically indicated.
- e. Hematology, coagulation, serum chemistry, and urinalysis.
- f. Urine pregnancy tests will also be completed whenever one menstrual cycle is missed during the active treatment period (or when potential pregnancy is otherwise suspected) and at the end of the study to confirm the subject has not become pregnant during the study. Pregnancy tests may also be repeated as per request of the ethical board or if required by local regulations.
- g. Investigational product will be given intradiscal by injection under fluoroscopic or CT visualization and guidance and confirmed by MRI.
- h. Performed at the time of the clinical visit only.

**Appendix 2: Screening and Clinical Laboratory Assessments**

### **Appendix 3: Definition**

#### **Adverse event (AE)**

An AE is defined as any untoward medical occurrence in a subject administered a pharmaceutical product during the course of a clinical investigation. An AE can therefore be any unfavorable and unintended sign, symptom, or disease temporally associated with the use of a study drug, whether or not thought to be related to the study drug.

#### **Adverse Events of Special Interest**

The following AEs will be considered an AESI:

1. MRI or X-ray findings of Modic changes, reduction of disc height, or evidence of lumbar instability, or any other acute MRI or X-ray changes from baseline images deemed significant by the central reader/spine imaging specialist.
2. Exacerbation of back or leg pain meeting at least 1 of the following criteria:
  - a) Increase in average daily leg or back pain score by  $\geq 3$  to 6 or above on the numerical rating scale for at least 5 days out of a week
  - b) Increase in average daily pain level associated with a new onset of focal neurological symptoms such as numbness and/or tingling or weakness lasting for  $> 5$  days.
3. New onset of neurological symptoms associated with objective changes on neurological examination (weakness, sensory deficit, changes in deep tendon reflexes) whether or not associated with increase in pain level.
4. Any deterioration of subject's condition that in the investigator's judgment requires:
  - a) Emergency MRI
  - b) Epidural steroid injection/selective nerve root block, facet block, or surgical intervention.

#### **Serious Adverse event (SAE)**

The investigator is responsible for determining whether an AE meets the definition of an SAE. An SAE is any AE occurring from ICF signing through final study visit, at any dose, that results in any of the following outcomes:

- Death
- A life-threatening event, defined as an event in which the subject was at risk of death at the time of the event
- Inpatient hospitalization or prolongation of existing hospitalization
- A persistent or significant disability/incapacity
- A congenital anomaly/birth defect in a child or fetus of a subject exposed to the study drug

- Important medical events that may not result in death, be life-threatening, or require hospitalization may be considered an SAE when, based upon appropriate medical judgment, they may jeopardize the subject and may require medical or surgical intervention to prevent any of the outcomes listed in this definition. Examples of such medical events include allergic bronchospasm requiring intensive treatment in an emergency room or at home, blood dyscrasias or convulsions that do not result in inpatient hospitalization, or the development of drug dependency or drug abuse.

### **Assessing Severity**

The severity of an AE will be graded according to the following definitions:

- Mild: The subject experiences awareness of symptoms but these are easily tolerated or managed without specific treatment
- Moderate: The subject experiences discomfort enough to cause interference with usual activity, and/or the condition requires specific treatment
- Severe: The subject is incapacitated with inability to work or do usual activity, and/or the event requires significant treatment measures.

### **Assessing Causality**

The relationship of the event to the study drug should be determined by the investigator according to the following criteria:

- Not related: The event is most likely produced by other factors such as the subject's clinical condition, intercurrent illness, or concomitant drugs, and does not follow a known response pattern to the study drug, or the temporal relationship of the event to administration of study drug makes a causal relationship unlikely.
- Possibly related: The event follows a reasonable temporal sequence from the time of drug administration, and/or follows a known response pattern to the study drug, but could have been produced by other factors such as the subject's clinical condition, intercurrent illness, or concomitant drugs.
- Probably related: The event follows a reasonable temporal sequence from the time of drug administration, and/or follows a known response pattern to the study drug, and cannot be reasonably explained by other factors such as the subject's clinical condition, intercurrent illness, or concomitant drugs.

## Appendix 4: Halting Rules

The AEs or imaging abnormalities described below will be defined in this study as a halting rule (HR). If a HR occurs in any subject during the dose escalation phase of the study, further recruitment and dosing of the current study cohort will be held until the event is assessed by the Data and Safety Monitoring Board (DSMB). The DSMB will make a recommendation regarding continuation of the study and/or escalation to the next dose cohort when one of the following events occurs:

- Neurologic deficit consistent with cauda equina syndrome or myelopathy
- Exacerbation of radicular symptoms associated with onset of a new motor deficit in one or both legs following administration of study drug
- Modic changes consistent with significant endplate edema or sclerosis compared to baseline, as determined by an expert spine radiologist
- Loss of height of the disc of > 30% relative to the baseline and defined as the average of anterior and posterior disc height evaluated by X-ray
- Evidence by X-ray of lumbar segmental instability at the treated segment defined as either:
  - Anterior translation of the posterior edge of the superior vertebral body relative to the posterior edge of the inferior vertebral body increase from baseline greater than 3mm is considered strong evidence of instability.
  - Sagittal rotation change from extension to flexion of >5° (as measured by the Dupuis method) [2] is weak evidence of instability, and without observed translation as defined above, will require further evaluation before it would be considered a halting event.

NOTE: if the subject's condition does not permit the acquisition of flexion and extension films, instability will be evaluated solely on the basis of translation on the lateral view, as described above.

- Destructive cartilage endplate changes as confirmed by MRI.

Once the last 13-week follow up period after the last dose cohort has occurred, any future instances of these events will be reported as AESI, but will not be treated as a HR.

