1 SYNOPSIS

Protocol Title:	Open-label, non-controlled, single-ascending dose study to evaluate safety, tolerability, pharmacokinetics, and exploratory efficacy of KTP-001 in subjects with lumbar disc herniation
Sponsor:	Teijin America, Inc.
Study Phase:	Phase 1/2
Indication:	Herniated lumbar disc
Objectives:	
The primary objective of this study is:
 
 • To evaluate the safety and tolerability of a single intradiscal injection of KTP-001 in subjects with a single herniated lumbar disc. 
The secondary objectives of this study are:
 
 • To determine the pharmacokinetics (PK) of KTP-001 in the serum of circulating blood after intradiscal injection of the study drug. • To determine the presence of anti-KTP-001 antibody in the serum of circulating blood after intradiscal injection of the study drug. 
The exploratory objectives of this study are:
 
 • To explore the pharmacodynamics (PD) of keratan sulfate in the serum of circulating blood after intradiscal injection of the study drug. • To assess changes in pain, neurologic examination, disability, magnetic resonance imaging (MRI) and X-ray assessments, Quality of Life (QOL), and patient global impression of change (PGI-C) scores in subjects receiving study drug.
Number of Sites:	This study will be conducted at approximately 8 sites in the United States.
Study Design:	This study is designed as an open-label, non-controlled single ascending dose study. Twenty-four subjects with a diagnosis of a single herniated lumbar disc will be divided into 4 cohorts of 6 subjects. Dose escalation will begin with a 5 µg intra-disc administration. After all subjects in the first cohort have reached the Week 13 assessment, relevant safety data will be reviewed. If adequate safety and tolerability has been demonstrated, KTP-001 dose escalation will continue in subsequent escalating doses of 15, 50, and 150 µg/disc with safety reviews conducted prior to each dose escalation.
Planned Sample Size:	Approximately 48 subjects will be screened to ensure that 24 subjects are enrolled into this study. Subjects who discontinue from the study after enrollment but prior to receiving study drug will be replaced to ensure that at least 6 subjects are treated in each of the 4 cohorts.

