5.1.3 Halting Rules

The AEs or imaging abnormalities described below will be defined in this study as a halting rule (HR). If a HR occurs in any subject during the dose escalation phase of the study, further recruitment and dosing of the current study cohort will be held until the event is assessed by the DSMB. The DSMB will make a recommendation regarding continuation of the study and/or escalation to the next dose cohort when one of the following events occurs:

- Neurologic deficit consistent with cauda equina syndrome or myelopathy
- Exacerbation of radicular symptoms associated with onset of a new motor deficit in one or both legs following administration of study drug
- Modic changes consistent with significant endplate edema or sclerosis compared to baseline, as determined by an expert spine radiologist
- Loss of height of the disc of > 30% relative to the baseline and defined as the average of anterior and posterior disc height evaluated by X-ray
- Evidence by X-ray of lumbar segmental instability at the treated segment defined as either:
 - Anterior translation of the posterior edge of the superior vertebral body relative to the posterior edge of the inferior vertebral body increase from baseline greater than 3mm is considered strong evidence of instability
 - Sagittal rotation change from extension to flexion of >5° (as measured by the Dupuis method)^[11] is weak evidence of instability, and without observed translation as defined above, will require further evaluation before it would be considered a halting event

NOTE: if the subject's condition does not permit the acquisition of flexion and extension films, instability will be evaluated solely on the basis of translation on the lateral view, as described above

- Destructive cartilage endplate changes as confirmed by MRI.

Once the last 13-week follow up period after the last dose cohort has occurred, any future instances of these events will be reported as AESI, but will not be treated as a HR. Further details on the role of the DSMB to evaluate study conduct will be provided in a separate DSMB charter.

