#### **6.7 Data Endpoints and Analyses**

The primary objective endpoints analysis and safety endpoints will be performed based on safety population. Full analysis set and per protocol set will be used as the analysis population for secondary and exploratory efficacy endpoints. All the results will be summarized by cohort. Descriptive summary statistics mentioned in the [Section 4.0](#) will be used for the analysis. Comprehensive listings of all data will be presented.

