### **6.7.1 Analysis of Primary Endpoint - Safety**

Primary endpoint of this study is safety and tolerability. The following are the primary safety endpoints:

- Adverse events (AE)
- Serious adverse events (SAE)
- Deaths or discontinuations due to AEs (including subjects who have lumbar surgery) that occur after administration of study drug.
- Change and shifts from baseline in vital signs of
  - Heart rate
  - Systolic/Diastolic blood pressure
  - Respiratory rate
  - Body temperature
- Tabulation of number of subjects with "substantial" increases or decreases in BP (>20 mmHg) and heart rate (>15 bpm)
- 12-lead Electrocardiograms (ECGs)
  - Heart rate
  - Rhythm
  - PR
  - RR
  - PQ
  - QT intervals
  - QTc [Bazett's and Fridericia's]
  - QRS
- Clinical laboratory tests
  - Hematology
  - Serum chemistry
  - Coagulation
  - Urinalysis
- Data from MRI and X-ray (including morphological assessment)
- Data from neurologic assessments
  - Positive straight-leg raising or femoral stretch test

- Alteration of deep tendon reflexes (knee and ankle)
- Sensory, or motor deficits in the lower extremities.
- Abnormalities in physical examinations
- Number of subjects who experienced any AEs defined as a halting rule
- Serum anti-KTP-001 antibody analysis by electrochemiluminescence

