#### **6.7.1.8 Halting rules**

The number of subjects with AEs defined as halting rules (HRs) will be described and evaluated. Halting rule is explained in the [appendix 4](#).

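### Read literally, the halting-rule count by cohort closes on one study-wide date, giving the 150 µg cohort the shortest window; SAP 6.7.1.8 should count by time since injection

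*SAP*

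**What the plan says.** SAP 6.7.1 lists among the primary safety endpoints: "Number of subjects who experienced any AEs defined as a halting rule". SAP 6.7.1.8 gives the analysis in one line, "The number of subjects with AEs defined as halting rules (HRs) will be described and evaluated", and refers to Appendix 4 for the meaning of a halting rule. SAP 6.7 adds: "All the results will be summarized by cohort". No counting window, person-time or time-since-injection rule is given for this endpoint.

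Appendix 4 lists the qualifying neurologic and imaging events. The hold on recruitment and dosing applies as follows: "If a HR occurs in any subject during the dose escalation phase of the study". Subjects in earlier cohorts therefore stay under the rule while later cohorts are dosed. The appendix then closes the rule for the whole study at one point, "Once the last 13-week follow up period after the last dose cohort has occurred", after which "any future instances of these events will be reported as AESI, but will not be treated as a HR". Protocol 5.1.3 has the same cut-off.

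On timing, the Protocol synopsis says that the 24 subjects "will be divided into 4 cohorts of 6 subjects". The synopsis and SAP 3.1 require every subject in a cohort to reach Week 13 before the DSMB decides on the next dose. Post-dose X-ray and MRI are scheduled at Week 13 and Months 6, 12, 18 and 24 in every cohort.

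**The concern.** The cut-off makes sense for running the study: once the last cohort has passed Week 13, there is no dosing left to hold. The difficulty is that the SAP uses the same appendix to define an analysis endpoint. A study-wide date falls at a different time since injection in each cohort, latest for 5 µg and earliest for 150 µg. A disc-height loss above 30% first seen on the Month 6 X-ray could then count at 5 µg but not for the last-dosed subject at 150 µg.

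Safety and tolerability are the primary objective and there is no control arm, so comparison across doses carries most of the information. A count with its shortest window at the top dose could make a flat relation with dose look falling, or flatten a rising one, if a material share of events is first detected after Week 13.

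**Working it through.** The documents state no time at risk for this endpoint, so there is no figure to reproduce. The windows below follow from the schedule.

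**Inputs.** Four sequential cohorts (Protocol synopsis). Week 13 must be reached by all subjects of a cohort before the next is dosed (synopsis; SAP 3.1). Cut-off at the end of the last cohort's 13-week follow-up (SAP Appendix 4). Week 13 visit window ±5 days (Protocol 11.7). Imaging at Weeks 13, 26, 52, 78 and 104.

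**Step 1: minimum window.** For the last-dosed subject of cohort k, with no recruitment or DSMB time, the window is (5 − k) × 13 weeks. If every Week 13 visit falls 5 days early (day 86), it is (5 − k) × 86/7. If each further cohort adds an assumed L weeks for recruitment and DSMB review, it is (5 − k) × 13 + (4 − k) × L.

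| Case | 5 µg | 15 µg | 50 µg | 150 µg |
|---|---|---|---|---|
| Nominal minimum | 52 | 39 | 26 | 13 |
| All visits 5 days early | 49.1 | 36.9 | 24.6 | 12.3 |
| L = 4 (assumed) | 64 | 47 | 30 | 13 |
| L = 8 (assumed) | 76 | 55 | 34 | 13 |
| L = 13 (assumed) | 91 | 65 | 39 | 13 |

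Delay lengthens only the earlier cohorts' windows. Within any cohort, subjects dosed before the last one gain their enrolment lead. For example, if Cohort 4 took an assumed 13 weeks to enrol, its first subject would have 13 + 13 = 26 weeks and would reach the Month 6 visit.

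**Step 2: scheduled imaging inside the nominal window.** If a scan on the cut-off day counts, the last-dosed subjects have 3, 2, 2 and 1 scans. If it does not, they have 2, 2, 1 and 0. The last 150 µg subject's only scan in the window thus sits on the boundary, and central reading comes later still. The SAP does not say whether it counts.

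**Step 3: effect on the count (illustration).** Assume the same constant risk p per 13 weeks at every dose, and give all six subjects of a cohort its nominal minimum window. The expected number of subjects is 6 × [1 − (1 − p)^m], with m = 4, 3, 2, 1.

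- p = 2%: 0.47, 0.35, 0.24, 0.12
- p = 5%: 1.11, 0.86, 0.59, 0.30
- p = 10%: 2.06, 1.63, 1.14, 0.60

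At p = 5%, the chance of at least one such subject is 1 − 0.95^24 = 71% at 5 µg and 1 − 0.95^6 = 27% at 150 µg. For the expected counts to match, the 150 µg cohort would need a 13-week risk of 1 − 0.95^4 = 18.5%, about 3.7 times 5%. Counted over a common 13 weeks, every cohort would expect 6 × 0.05 = 0.30.

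**Step 4: the other extreme.** If all events occur and are detected by Week 13, the extra weeks at lower doses add nothing and the bias is near zero. The documents give no event timing with which to choose between the two.

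**The case against.** The strongest reply is that the cut-off is operational only. Appendix 4 opens with an undated definition, the endpoint counts events *defined as* halting rules, and only the last paragraph speaks of events *treated as* one. On that reading, a late event still meets the definition and is counted, but triggers no hold. This is a reasonable reading and may be the intended one. However, 6.7.1.8 points to the whole appendix without exception, so two programmers could produce different primary tables.

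Second, late events are not lost. SAP 6.7.1.5 and 6.7.1.6 summarise imaging and neurologic results by cohort at every scheduled visit, which compares doses at equal times since injection. The AESI table has no calendar cut-off, its first item uses Appendix 4 definitions, and listings cover the rest. All of this stands. What is missing is a count of subjects meeting the halting criteria over equal follow-up. The imaging and neurologic outputs are summaries by visit. The AESI category is broader, adding other imaging changes, pain exacerbation and further neurologic events, and is tabulated by system organ class and preferred term.

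Third, the size is unknown. Protocol 9.6.2 centres the MR safety evaluation on Modic changes at Week 13, so early detection may dominate. That also stands. Equally, no post-dose scan is scheduled before Week 13, so first detection at a later scan is plausible.

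Finally, this is one descriptive count among many, with six subjects per cohort and no hypothesis test. Escalation rests on DSMB review at each cohort's Week 13, not on the final table. This limits the consequence and argues against treating the point as critical.

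**Conclusion.** The point holds conditionally, as something that should be fixed. If the last paragraph of Appendix 4 limits the endpoint, the last-dosed subjects at 5, 15, 50 and 150 µg have nominal minimum windows of 52, 39, 26 and 13 weeks (about 49, 37, 25 and 12 with every Week 13 visit 5 days early). The count would favour the top dose to the extent that events are first detected after Week 13. At the nominal minimum, the distortion between 5 and 150 µg runs from near zero, with all detection by Week 13, to about 3.7-fold under an assumed equal, constant 5% risk per 13 weeks.

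A reader might infer that late structural changes at 150 µg are removed from the safety report, or that a flat dose relation must appear to fall. The documents support neither. Late events appear in several by-cohort outputs, an operational-only reading is open, some 150 µg subjects may reach Month 6 before the cut-off, and no event timing is given. What is established is that a primary safety count has no stated window and, on its literal definition, has unequal ones.

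**What to change.** Leave the operational hold as it is and change only the analysis text. In SAP 6.7.1.8:

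- Count, by cohort, subjects whose findings meet any Appendix 4 criterion, by time since injection: (a) through the Week 13 visit, including its visit window and the reading of that visit's scans, and (b) through Month 24.
- State that the last paragraph of Appendix 4 does not limit these counts.
- List separately which events triggered a hold.

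The cost is SAP wording and an extra table column. No new data are needed, because the same images and examinations are scheduled in every cohort. The top-dose count may look less favourable than under the literal cut-off.
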